^e Contact 7 is the last Follow-up contact; it should occur approximately 10 days after Contact 6.

CGM Initiation in People with T2D

4. Schedule of Activities

	Baseline (10 days)	Intervention (~50 days including the 10-day post-intervention period)			Post-Intervention Assessment & Study Completion (10 days)		Follow-Up Assessment (10 days)	
Study Phase	Phase 1					Phase 2		
Contact	1	2	3	4	5	6	7	
Visit Type	Clinic (Day -11)	Clinic	Remote	N/A	Clinic	Clinic	N/A	
Study Day(s)¹	-11 to -1	0	14 (+7)	40 (+7)	50 (+7)	170 (+14)	180 (+7)	
Consent	X							
HbA1c	X				X	X		
Demographics	X							
Up to 10-Day Blinded G7 CGM Assessment	X					X		
Blinded G7 CGM Data Downloaded and Saved		X					X ⁶	
ASA24 Diet Recall	X	X ⁴		X ⁵	X	X ⁵	X	
DietID Diet Recall	X				X			
PROs: Diabetes Distress, Diet Adherence, Efficacy Surveys, and Diabetes Self Care	X				X	X		
PROs: Intervention Fidelity and Post-Intervention Surveys					X			
Diabetes Medication Assessment	X	X	X		X	X		

CGM Initiation in People with T2D

BP, Weight, Height ²	X				X	X	
Randomization ³	X ³						
Participant Receives Randomization Assignment		X ³					
CGM Initiation / Education (based on randomization arm)		X	X				
Continuous Real-time G7 CGM Use							
Real-time G7 CGM Data Downloaded and Saved			X		X		
Up to 10-Day Real-time G7 CGM Assessment Begins				X			
Adverse Events						X	

¹ If indicated, up to seven or 14 days can be added to or subtracted from the specified contact date to allow for scheduling flexibility; ² Height at baseline only; ³ Randomization occurs for scheduling purposes only; the randomization assignment is not shared with the participant during Contact 1 and will not be shared at Contact 2 until a minimum of 7 days of blinded G7 CGM data are confirmed; ⁴ This ASA24 is considered part of the baseline assessment and should occur before any of the Contact 2 activities ⁵ Two ASA24 assessments on non-consecutive days should be completed during the post-intervention and follow-up periods, one should occur on approximately Day 40 and Day 170 and one on approximately Day 50 and Day 180 ⁶ Participants may have the option to return receivers via postal mail; if this occurs, data download will be delayed
							

5. Phase 1 Background

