In alignment with guidance from the international consensus statement on CGM use in clinical trials,²⁶ CGM devices will be kept consistent between study arms and throughout the study.

The Dexcom G7 system will be used during the baseline, intervention, post-intervention, and follow-up assessment periods. The G7 system is commercially available and includes an all-in-one wearable sensor with transmitter, an overpatch, and either a Dexcom receiver device or two associated smartphone applications, G7 and Clarity, which send data via cloud. The G7 system will be used in accordance with the manufacturer-provided instructions throughout the study; however, during the baseline period and follow-up period, the glucose data will be physically blinded, and participants will not be able to see glucose data.

Phase 1: Baseline Period

Baseline assessments will begin during Contact 1. Any participant who meets HbA1c criteria is considered enrolled. Participants who do not meet HbA1c criteria will be considered a screen failure and will not be considered enrolled in the study. Demographic and anthropometric information will be assessed to describe the participants. At a minimum, age at enrollment, race, ethnicity, year of type 2 diagnosis, gender identity, sex assigned at birth, weight, height, blood pressure, medication assessment, education, and food security status will be collected.

Baseline assessments also include dietary assessments, PRO surveys, and a 10-day blinded G7 CGM assessment. Study staff will apply the G7 sensor for the participant and pair it with a Dexcom receiver

CGM Initiation in People with T2D

that will be physically blinded by the study team. The participant will receive instructions on how to care for the receiver and will wear the G7 sensor for up to 10 days; however, participants will not be able to see their glucose data during this time. Participants will be instructed to contact the study team if the sensor comes loose or falls off earlier than 10 days or for any other sensor-related concerns. A minimum of seven days of G7 sensor data is required. If a participant does not capture at least seven days of sensor data, the participant will have an option for study staff to pair another G7 sensor with the physically blinded Dexcom receiver, or the participant can choose to exit the study.

Randomization

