During contact 6 (approximately Day 170), participants will be asked to report any serious changes to health, changes to diabetes-related medications, and diabetes device use during the previous 4 months. Participants will complete additional assessments and study staff will apply a 10-day G7 sensor paired with a physically blinded receiver; the process and devices are the same as baseline.

The participant will receive instructions on how to care for the receiver and will wear the G7 sensor for up to 10 days; however, participants will not be able to see their glucose data during this time. Participants will be instructed to contact the study team if the sensor comes loose or falls off earlier than 7 days or for any other sensor-related concerns. If a participant reports fewer than seven days of sensor wear, the participant will have an option to return to the clinic so that study staff can pair another G7 sensor with the physically blinded receiver.

On approximately Day 180, participants will receive a study reminder to complete a final ASA24 diet recall and to return their physically blinded receiver to the study team (e.g. postal mail or in person).

Detailed Schedule of Activities

The study includes approximately seven contacts between study staff and study participants.

Contact	Key tasks
Contact 1: Baseline assessments Day -11 to Day -1 (plus additional days, if needed, to obtain at least seven days of G7 sensor data)	
• Preliminary eligibility confirmed, consent signed• HbA1c to confirm eligibility^a• Demographic/Diabetes self-care data assessment• Diabetes medication assessment• Height, weight, BP• Study team applies G7 sensor and pairs it with a physically blinded Dexcom receiver• ASA24 and DietID assessments

CGM Initiation in People with T2D

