
Baseline Assessment
	
 • PRO surveys (Diabetes distress, diet adherence, efficacy) • Participant wears G7 sensor paired with a physically blinded Dexcom receiver for up to 10 days and returns to clinic^b • Participant completes second ASA24 recall immediately before Contact 2 
^a As needed, participants will be contacted by study staff if their HbA1c does not meet inclusion criteria; instructions for sensor removal and options for returning the blinded receiver to the study team will be provided.
 
^b At least seven days of G7 sensor data must be obtained on the physically blinded Dexcom receiver. If a participant contacts the clinic to report the sensor has fallen off early/failed in fewer than seven days, the participant will be provided an option to return to clinic to pair another G7 sensor with the physically blinded Dexcom receiver, or the participant may choose to exit the study. Data from more than one G7 sensor may be an option to reach a total of seven days.

Contact 2: Participant receives randomization assignment and intervention begins
 
Day 0
 
Intervention
	
 • Eligible participants return to clinic with the physically blinded Dexcom receiver • Study team confirms at least seven days of CGM data were obtained* • Study team saves participant’s CGM data • Diabetes medication assessment • Participant receives randomization assignment • Participant applies G7 sensor and pairs it with apps on their personal cell phone • Participant receives CGM instruction based on study arm assignment, NFA or SDA • Participant wears the G7 sensor and uses the real-time glucose data from the associated apps until study completion • Study team documents measures of intervention fidelity 
*Confirmation of at least seven days of G7 sensor data is required before the participant can receive their randomization assignment. If seven days of G7 sensor data are not obtained, no Contact 2 assessments will be completed. The participant will be provided an option to pair another G7 sensor with the physically blinded Dexcom receiver and return for Contact 2 assessments in approximately 10 days, or the participant can choose to exit the study. Data from more than one G7 sensor may be an option to reach a total of seven days.

CGM Initiation in People with T2D

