
Contact 3: Remote Follow-up
 
Day 14 (+7 days)
 
Intervention
	
 • Study team saves participant’s CGM data from Clarity website immediately before remote contact • Study staff contacts participant • Diabetes medication assessment • Study staff reviews CGM data with participant and reinforces the NFA or SDA messages based on participant’s randomization arm • Participant wears the G7 sensor and uses the real-time glucose data from the associated apps until study completion • Study team documents measures of intervention fidelity

Contact 4: Post-intervention assessments begin
 
Day 40 (+7 days)
 
Intervention
	
 • Participant receives reminder from study team on approximately Day 40 to: 
 ○ Wear G7 sensor and use data from the associated apps for final 10-days of the study ○ Complete first post-intervention ASA24 diet recall

Contact 5: Post-intervention assessments ends
 
Day 50 (+7 days) (plus additional days, if needed, to obtain at least seven days of G7 sensor data)
 
Post-Intervention Assessments & Study Completion
	
 • Study team confirms at least seven days of G7 CGM data collected between approximately Day 40 and Day 50 
 ○ If a participant has fewer than seven days of CGM data, the participant will be provided an option to continue in the study until seven days of data are obtained or the participant can choose to exit the study • Study team saves participant’s CGM data from Clarity website • Participant completes post-intervention assessments, including: 
 ○ HbA1c ○ Diabetes medication assessment ○ Weight, BP ○ Complete second ASA24 diet recall and DietID assessment ○ PRO surveys (Diabetes distress, diet adherence, efficacy, intervention fidelity, post-intervention survey)

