
Contact 6: Follow-up assessments begin
 
Day 170 (+14 days)
 
Follow-up Assessment
	
 • HbA1c • Diabetes medication assessment • Adverse event assessment • Weight, BP • Complete first follow-up period ASA24 diet recall • PRO surveys (Diabetes distress, diet adherence, efficacy, diabetes self-care) • Study team applies G7 sensor and pairs it with a physically blinded Dexcom receiver • Participant wears G7 sensor paired with a physically blinded Dexcom receiver for up to 10 days* 
*If a participant contacts the clinic to report the sensor has fallen off early/failed in fewer than seven days, the participant will be provided an option to return to clinic to pair another G7 sensor with the physically blinded Dexcom receiver. A

CGM Initiation in People with T2D

	minimum of seven days of sensor data is desired, but not required. Data from more than one G7 sensor may be an option to reach 10 days.
Contact 7: Follow-up assessments end Day 180 (+7 days) (plus additional days, if needed, to obtain at least seven days of G7 sensor data) Follow-up Completion	
• Participant receives reminder from study team on approximately Day 180 to:
○ Return the physically blinded receiver to the clinic (e.g. postage-paid envelope)• Complete second follow-up period ASA24 diet recall

16. Study Device Management

Participants who terminate early or who are withdrawn at any point during Phase 1 or Phase 2 will be asked to return the Dexcom G7 receiver to the clinic, if applicable. Any unused G7 sensors may be returned to the clinic or disposed of properly by participant.

17. Early Termination and Participant Withdrawal

A participant can choose to terminate study participation and exit the study at any time and for any reason. Participants who request early termination will be asked for a reason for their decision. A participant can be withdrawn from the study with or without their consent if deemed necessary based on adverse event(s) or for any other reason deemed appropriate by Investigators, such as non-compliance with study instructions. If a participant chooses early termination or is withdrawn, the Investigators will decide whether the participant may be eligible to complete final assessments.

18. Lost to Follow-Up

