Hypothesis (alternative): Participants randomized to a nutrition-focused approach (NFA) will show a higher total HEI score during the post-intervention than participants randomized to a self-directed approach (SDA).

Phase 2 Statistical Hypothesis

Primary Endpoint: Change in CGM-derived TIR (% time with glucose 70-180 mg/dL) from post-intervention to follow-up

Hypothesis (alternative): Participants will show a reduction in CGM-derived TIR from post-intervention to follow-up.

Sample Size Determination

Phase 1 of the study will enroll at least N=132 participants with the expectation for an analytic sample size of N=120. This sample size is based on the N needed to adequately power the primary hypothesis with a realistic and clinically meaningful effect size for % TIR. Specifically, existing research on CGM initiation in people with T2D shows mean TIR of 59% with SD of 25% after intervention.

An analytic sample size N=60 participants per arm has 80% power ($\alpha=.05$, two-sided) to detect an absolute differential change by study arm (i.e., more improvement in the NFA than SDA arm) of 12.9% from baseline to post-intervention (day 50). Justification to support a 12.9% difference in TIR requires converting A1c study data to TIR. The Mobile study showed a 0.4% decrease in A1c after CGM initiation in people with T2D using insulin; we expect a slightly smaller, 0.3%, improvement in our non-insulin using population. An eight-week nutrition intervention study showed a 1.2% decrease in A1c with the DASH diet; we expect a more conservative, 0.7%, improvement (in the NFA arm).

Using the A1c to TIR conversion (0.5% A1c reduction equals 10% TIR increase) suggests a 14% increase (difference) in TIR.

To account for approximately 10% attrition, the enrollment target will be set at N=66 per arm; total N=132.

CGM Initiation in People with T2D

The Phase 2 sample is dependent on the number of participants that complete Phase 1 and continue through the Phase 2 follow-up assessment period. It is expected that 90% of those completing Phase 1 (n=54/arm) will complete Phase 2 and have CGM data at follow-up. It is expected that 85% of those completing Phase 1 (n=51/arm) will complete Phase 2, have at least 7 days of CGM data at follow-up, refrain from CGM use during the follow-up period, and have no glucose-lowering medication changes during the follow-up period.

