With an expected sample size of n=54 per arm for the intention to treat (ITT) sample in Phase 2, the primary analysis has 80% power ($\alpha=.05$, two-sided) to detect an absolute change for pooled study arms of 0.27 standard deviation units of change in TIR from the end of the intervention to follow-up. For within-arm tests of change in this sample the primary analysis has 80% power ($\alpha=.05$, two-sided) to detect an absolute change within a study arm of 0.39 standard deviation units of change in TIR from the end of the intervention to follow-up.

Populations for Analysis

The analysis for Phase 1 will follow a modified intention to treat perspective, with an analysis of CGM metrics that includes only participants with at least seven days of CGM data at both baseline (approximately day -11 to -1) and post-intervention (approximately day 40 to 50).

The analysis for Phase 2 will follow a modified intention to treat perspective, with an analysis of CGM metrics that includes only participants with at least seven days of CGM data at both post-intervention and follow-up. This sample is utilized to assess the effect of discontinuation of CGM utilized in phase 1. A per-protocol (PP) analytic sample will consist of participants with at least seven days of CGM data at both post-intervention and follow-up who did not use CGM, and who did not require changes to glucose-lowering medications during the follow-up period. This PP sample is utilized to assess the effect of discontinuation on patients not utilizing CGM and having no medication adjustments during the follow-up period.

General Approach for Statistical Analyses in Phase 1

Baseline characteristics of study participants will be summarized with mean and standard deviation for interval data and proportions for categorical data. For analyses that do not concern total HEI or HEI component scores, the analytic models will utilize general and generalized linear mixed model repeated measures analysis to estimate differential change by study arm from baseline to post-intervention period. The link function and error distribution selected for each model will be based on the distribution of the endpoint. Each model will include fixed effects for study arm, time, their interaction, variables used in stratification, and a random intercept for patient. Each model will report the model-derived estimate (and 95% confidence interval) for the endpoint by study arm and by time period (baseline, day 50).

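### Contact 6 treats seven days of follow-up CGM data as optional although the Phase 2 CGM analyses require them, and no staff check of follow-up data is stated

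*Combined protocol and SAP*

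**What the plan says.** **Visit rule.** In section 15, Detailed Schedule of Activities, the Contact 6 note says a "minimum of seven days of sensor data is desired, but not required".

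**Analysis rule.** In section 23, Populations for Analysis, the Phase 2 modified ITT analysis of CGM metrics "includes only participants with at least seven days of CGM data at both post-intervention and follow-up". The per-protocol set carries the same condition and adds no CGM use and no change in glucose-lowering medication.

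**Extension.** The Contact 7 heading and schema footnote c (section 3) both allow the follow-up window to be lengthened when fewer than seven days have been captured.

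**Checks at the two earlier windows.** At Contact 2: "Study team confirms at least seven days of CGM data were obtained". At Contact 5: "Study team confirms at least seven days of G7 CGM data collected between approximately Day 40 and Day 50". In both cases further wear is offered if the data fall short.

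**Follow-up.** The Phase 2: Follow-Up Period text offers a repeat sensor under this condition: "If a participant reports fewer than seven days of sensor wear". Contact 7 has no clinic visit type. It is a reminder to return the receiver and complete a diet recall. Section 4, note 6 adds: "Participants may have the option to return receivers via postal mail; if this occurs, data download will be delayed".

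**Sample size.** Section 23, Sample Size Determination, expects that 90% of Phase 1 completers (54 per arm) "will complete Phase 2 and have CGM data at follow-up". It labels this the ITT sample and attaches detectable changes of 0.27 SD (pooled) and 0.39 SD (within arm). A second group, 85% or 51 per arm, must have seven days of data and also meet the two extra per-protocol conditions.

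**The concern.** Staff who follow Contact 6 as written can accept six days of follow-up data without learning from that text that the participant then leaves every Phase 2 CGM analysis, including the primary endpoint. Participants are blinded to their glucose readings, and nobody is told to look at the stored data while repeat wear could still be arranged. A shortfall may therefore come to light only after the receiver is back, possibly by post.

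Two things are at stake. One is the loss of participants whose data could have been completed. If short wear goes with poorer self-management, that loss would not be random with respect to change in TIR. The other is that the stated detectable changes belong to a group defined by any follow-up CGM data, while the analysis uses a subset of it. No expected size is given for that subset.

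**Working it through.** **1. The three CGM windows side by side**

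| Window | Stated staff check of seven days | What leads to further wear |
|---|---|---|
| Baseline | Yes, at Contact 2, before the assignment is disclosed | Staff finding or participant report |
| Post-intervention | Yes, at Contact 5 | Staff finding |
| Follow-up | None stated; a download is marked at Contact 7 | Participant report |

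The extension provisions for follow-up do not say who establishes that fewer than seven days were captured, or when.

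**2. Reproducing the plan's detectable changes**

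Inputs from Sample Size Determination: two-sided alpha 0.05, power 80%, 60 per arm completing Phase 1, and 90% with follow-up CGM data. That gives 0.90 × 60 = 54 per arm, or 108 pooled.

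For a one-sample test of mean change, the normal approximation is d = (1.960 + 0.842)/√n.

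- n = 108: 2.802/10.392 = 0.270 SD
- n = 54: 2.802/7.348 = 0.381 SD

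Solving with the noncentral t distribution (n − 1 degrees of freedom, noncentrality d√n) gives 0.272 SD at n = 108 and 0.388 SD at n = 54. The stated 0.27 and 0.39 SD are reproduced.

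**3. Bounds for the seven-day set**

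The 85% group has 0.85 × 60 = 51 per arm (102 pooled). It meets the seven-day condition and two others, so the seven-day modified ITT set is at least that large. It is contained in the group with any follow-up data, so it is at most 54 per arm (108 pooled).

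| Set | n | Detectable change (t), SD | Power at the stated change |
|---|---|---|---|
| Pooled, upper bound | 108 | 0.272 | 79.4% for 0.27 SD |
| Pooled, lower bound | 102 | 0.280 | 77.1% for 0.27 SD |
| Within arm, upper bound | 54 | 0.388 | 80.3% for 0.39 SD |
| Within arm, lower bound | 51 | 0.400 | 78.0% for 0.39 SD |

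**4. Larger shortfalls (assumed)**

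The documents give no rate of short wear. The shares below are assumptions, applied to 108 and rounded.

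| Assumed share under seven days | Pooled n | Detectable change, SD | Power for 0.27 SD |
|---|---|---|---|
| 5% | 103 | 0.279 | 77.5% |
| 10% | 97 | 0.287 | 74.9% |
| 20% | 86 | 0.306 | 69.7% |

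**The case against.** The best defence is that the two rules do different jobs. At baseline, seven days are a condition for receiving the assignment. At follow-up there is nothing left to gate, and Contact 6 also collects HbA1c, weight, diet and patient-reported outcomes. Keeping a participant with short wear for those outcomes while leaving them out of the CGM analysis is coherent. That stands: a reader might infer a flat contradiction, and the text does not force one. It remains true that Contact 6 does not mention the consequence and sits awkwardly beside two provisions that extend the window to reach seven days.

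A reader might also infer that the extension cannot work. It can. Participants are told to call about any sensor concern, a repeat sensor is permitted, and a receiver returned in person could be read at once. Late reading is not peculiar to follow-up either, since the baseline receiver is read after wear and repeat wear still follows. What is missing is a stated check. One may exist in the study's manual of procedures or in the staff checklists for each contact, which are not among the documents.

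The baseline text asks participants to "contact the study team if the sensor comes loose or falls off earlier than 10 days", whereas the follow-up text uses seven days. This looks like a weakened trigger, but it has no bearing here: a sensor lost between days 7 and 10 can already have met the seven-day rule, and the baseline repeat-sensor note also uses seven days.

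**Conclusion.** The point holds as a minor one. The Contact 6 wording, the Contact 7 heading, schema footnote c and the Phase 2 analysis-set definition should be reconciled. Follow-up is the only CGM window without a stated staff confirmation of seven days, so some exclusions from the Phase 2 primary analysis are avoidable.

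The documents do not show that these exclusions are selective. They report neither how often wear falls short nor who is affected, so possibly non-random is as far as one can go. Nor do they support a claim that Phase 2 is materially underpowered. On the plan's own expectations the detectable change rises by at most 0.008 SD pooled (0.272 to 0.280) and 0.012 SD within arm (0.388 to 0.400). Those bounds rest on the sponsor's 85% and 90% expectations. Anything larger, such as 0.306 SD at a 20% shortfall, rests on an assumed rate.

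**What to change.** 1. In Contact 6, state that seven days are needed for inclusion in the Phase 2 CGM analysis and that participants with fewer days stay in for the other outcomes. Align the Contact 7 heading and schema footnote c with this.
2. Add one reminder about 3 to 5 days after the actual sensor application, asking whether the sensor is on and the receiver is working, and offer the repeat sensor that is already permitted. Time it from application, not from a study day: Contact 6 may move by up to 14 days, so a fixed date could fall before the sensor is applied.
3. When a receiver is returned in person, confirm seven days before closing follow-up and offer repeat wear if the data are short.
4. In Sample Size Determination, label 54 per arm as participants with any follow-up CGM data. Give the expected n and detectable change for the seven-day modified ITT set.

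The cost is some protocol wording, one extra message, an occasional additional sensor and clinic return, and a slightly less favourable stated detectable change. Shortfalls in receivers returned by post would still be found late. For those participants the reminder is the main safeguard.
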